### **2.4 Other Objectives for PrEP Comparison Component**

The other objectives of this component are:

- 2.4.1 To identify individual, social, and structural barriers and facilitators to PrEP uptake during pregnancy, and to adherence during pregnancy and postpartum.
- 2.4.2 To compare reported sexual risk behaviors and incidence of sexually transmitted infections, including HIV infection, among women who initiate PrEP during pregnancy versus women who decline PrEP.
- 2.4.3 To compare antiretroviral drug resistance among women and infants who acquire HIV with and without exposure to FTC/TDF for PrEP, including whether resistance was transmitted or acquired at time of transmission.
- 2.4.4 To compare bone density in women who initiated PrEP during pregnancy and women who decline PrEP.

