### **3.3 Standard of Care**

Sites will ensure that all participants access a basic standard of care (SOC) package which will generally include: a) HIV testing and risk reduction counseling at all visits; b) counseling and provision of contraception options; c) STI testing at screening, and STI testing and presumptive syndromic STI treatment, as needed; d) information on proper use of male and female condoms, including condom demonstrations, and provision of condoms; e) pregnancy testing; and f) discussion of HIV testing and prevention for their sexual partner(s) and referrals to local testing options for their partners. Refer to [Section 5.3.2](#) for additional details on counseling procedures.

At all visits, participants presenting with physical signs or symptoms, consistent with an STI will be referred for or provided with treatment as indicated. Participants with a laboratory diagnosis consistent with an STI will be referred for or provided with treatment as indicated. Due to the timing of specific lab testing, this may occur as an interim visit.

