Laboratory	
Collect blood for:
 

• HIV RNA test

• Store plasma for HIV drug resistance testing

• Rapid HIV test [see Section 6.3 in the event the test is (+)]

• Baseline TFV-DP level (DBS)

• Syphilis testing

• HSV2

 
Collect vaginal swab or urine for:
 

• Chlamydia and gonorrhea

 
Collect vaginal swab for:
 

• Microbiome

 
Collect rectal swab (if consented) for:
 

• Microbiome

Study Drug	
Cohort 1 only:
 

• Prescribe and dispense study drug

 A negative test result must be available prior to enrollment.

 Baseline sample must be collected prior to ingestion of study drug for Cohort 1 participants; the sample for Cohort 2 participants can be collected at any time and is required to confirm the participant is not receiving PrEP as standard of care.

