**Table 6: Other Outcome Measures – PrEP Comparison Component**

Other Measures – PrEP Comparison Component	
Objective	Outcome Measure
2.4.1	PrEP adherence: TDF-DP drug concentration level in DBS
2.4.2	Sexual risk behavior 
 
Any condomless vaginal or anal sex
 
Incident sexually transmitted infection defined as any new HSV, syphilis, chlamydia or gonorrhea infections during follow-up
 
Incident HIV infection
 

2.4.3	
 
Antiretroviral drug resistance: presence of virus resistant to TDF at time of HIV diagnosis
 

2.4.4	Bone mineral density – Mean maternal bone mineral density (g/m  ) based on DXA scan of the lumbar spine (LS-BMD) and hip (H-BMD) at delivery and 26 weeks postpartum

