### 9.2.4 Sample Size and Accrual

The PrEP Comparison Component will enroll a total of 350 (233 in Cohort 1 and 117 in Cohort 2) women over a 12-month period. Women will be followed through 26 weeks postpartum. Expected duration of follow-up for a given maternal participant is between 7 and 12 months depending on the gestational age of the pregnancy at enrollment. The following sample size and power calculations assume a final analysis sample of 300 women (200 in Cohort 1 and 100 in Cohort 2). The primary reason for the 2:1 enrollment into the two cohorts was to balance the need for a “No PrEP” comparison group (to provide the background rates for safety outcome measures) with the need for a large enough PrEP group to examine outcomes that would be restricted to women in that group (Adherence). To achieve this sample size at the analysis phase, this study will enroll ~350 women to accommodate a decrease of ~15% due to maternal attrition.

**Table 8** shows the expected precision of a range of PrEP adherence estimates across different sample sizes in Cohort 1. For example, with a sample size of 200 women in Cohort 1, the width of the 95% confidence interval for an estimated adherence rate of 75% is 13%.

**Table 8: Precision (shown as 2-sided 95% confidence intervals) of different estimates of the proportion with good adherence (for illustration, defined as meeting or exceeding the threshold corresponding to protective drug levels of TFV-DP) at different sample sizes for Cohort 1.**

% Adherent	Sample Size in Cohort 1			
	150	200	250	300
50	42-58%	43-57%	44-56%	44-56%
60	52-68%	53-67%	54-66%	54-66%
65	57-73%	58-72%	59-71%	59-70%
70	62-77%	63-76%	64-76%	65-75%
75	67-82%	68-81%	69-80%	70-80%
80	73-82%	74-85%	75-85%	75-84%

**Table 9** below shows the precision of estimates of safety outcomes (e.g. preterm birth) expected with a range of event rates and a sample size of 200 women in Cohort 1 and 100 women in Cohort 2. It is expected that the rates of these outcomes will be low particularly since this is a young group of healthy HIV uninfected women. To that end, a range of AE rates with corresponding confidence intervals is included in the protocol.

**Table 9: 95% Confidence Intervals for different possible event rates of safety outcomes in Cohort 1 (n=200) and Cohort 2 (n=100)**

Event Rate	95% Confidence Interval	95% Confidence Interval
	Cohort 1 (n=200)	Cohort 2 (n=100)
0.5%	(0, 2.8)	(0, 3.6)
2.0%	(0.5, 5.0)	(0.2, 7.0)
4.0%	(1.7, 7.7)	(1.1, 9.9)

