**Other Objective 2.4.2:**

Analyses to address this objective will include women in Cohort 1 and women in Cohort 2 in the analysis sample. Estimates of the proportion of women (at each visit) reporting condomless vaginal or anal sex at each visit that it is measured, and the proportion of visits with condomless vaginal or anal sex during pregnancy and during the postpartum period will be compared between Cohort 1 and Cohort 2 using chi square tests. To evaluate the association of Cohort (Cohort 1 vs. Cohort 2) with sexual risk behavior, GEE models will be fit, including adjustment for sociodemographic and behavioral factors that could confound the association of Cohort with risky sexual behavior. Cox regression methods will be used to estimate and compare the incidence rates of STIs in the antepartum period, the postpartum period, and throughout the study, among women with no STIs at enrollment in Cohort 1 and Cohort 2, adjusting for baseline confounders. Cox regression methods will be used to estimate and compare HIV incidence rates in pregnant and breastfeeding women who have initiated PrEP, in comparison to women who decline PrEP during the antenatal period.

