ALT, creatinine, CrCl	4mL		4mL		4mL	4mL	4mL	4mL		4mL	4mL	
Hepatitis B surface antigen	3mL										3mL	
Syphilis		1mL									1mL	
HSV2		1mL									1mL	
Glucose (random)	1mL											
Chlamydia/gonorrhea (vaginal swab or urine)		X									X	
Microbiome (rectal swabs); if consent provided		X			X  (EGA 34-38/40 weeks)				X		X	
Microbiome (vaginal swab)		X			X  (EGA 34-38/40 weeks)				X		X	
Vaginal secretion sampling for drug level					X  (EGA 34 -38/40 weeks)				X		X	
Urinalysis (protein and glucose)	X											
Ultrasound	X											
DXA scan (Hip, Lumbar Spine) 								X			X	
Pregnancy Test 										X	X	
Total maximum blood volume	15mL	12mL	14 mL	10mL	14mL	14mL	14mL	14mL	10mL	18mL 	20mL 	

 CASI is done at Week 26 visit only; CASI is not required at early D/C.

 If positive refer to [Section 6.3.1](#) and [Appendix IID](#) for additional procedures.

 Store plasma for HIV drug resistance testing at all visits indicated EXCEPT Screening.

 Blood collected for other tests will be used for the rapid HIV test; collection of additional blood is not required.

 Collect sample at any visit which occurs at an estimated 34 – 38/40 weeks' gestation.

 DXA scan at Wk 26/Exit and early D/C (as applicable) must be preceded by a pregnancy test.

 Urine (5mL) or blood (1mL) tests are acceptable. The total blood volume shown above accommodates collection of 1mL of blood, if needed. Note: *Pregnancy testing may be done prior to the DXA scan at Wk 26/Exit and Early D/C and does not need to be repeated.*

As per [Section 6.5](#)

## Appendix IIB (Schedule of Evaluations): Maternal PrEP Comparison Component Cohort 2

MATERNAL PROCEDURES:	SCR	Entry	Wk 4	Wk 8	Wk 12	Wk 24	Wk 36	L&D	PP Wk 6	PP Wk 14	PP Wk 26 / Exit and Early D/C	Step Change	
												Visit 1	Visit 2
Informed Consent	X												
Medical and Drug History	X	X	X	X	X	X	X	X	X	X	X	X	X
Physical Examination	X	X	X	X	X	X	X	X	X	X	X	X	X
Study drug dispensing													X
Assess for social harms			X	X	X	X	X	X	X	X	X	X	X
iNSC	X	X	X	X	X	X	X	X	X	X	X	X	X
CASI evaluations and COVID-19 questionannire		X	X	X	X	X	X			X	X 	X	X
Qualitative IDI							X				X		
HIV RNA  ; store plasma for HIV drug resistance testing 	4mL	6mL	6mL	6mL	6mL	6mL	6mL	6mL	6mL	6mL	6mL	6mL	
Rapid HIV 	X	X	X	X	X	X	X	X	X	X	X		X

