1.1 Purpose

This Primary Statistical Analysis Plan (SAP) describes the primary estimands and primary outcome measures that will address primary study objectives and interim monitoring of IMPAACT 2009. The Primary SAP includes general analytic approaches for all primary estimands, and primary outcome measures in the primary manuscript(s) or submitted to ClinicalTrials.gov (regardless of the reporting timeline). The Primary SAP facilitates discussion of the statistical analysis components among the lead study investigators and statisticians, helping them agree on the statistical analyses to be performed and presented in the primary analysis report.

The Analysis Implementation Plan (AIP) provides detailed outlines of tables, figures, and coding descriptions. A separate SAP will provide outlines of analyses for other objectives and outcome measures not included in the Primary SAP.

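### The STI incidence analysis keeps only women free of all tested STIs at entry, so one positive entry test removes a woman from the risk set for infections she can still acquire

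*Protocol*

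**What the plan says.** Protocol Section 2.4, Objective 2.4.2, is "To compare reported sexual risk behaviors and incidence of sexually transmitted infections, including HIV infection" between women who start PrEP in pregnancy and women who decline it. Nothing in the objective limits it to women free of STIs.

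Table 6 (Section 9.2.2.2) gives the outcome as "Incident sexually transmitted infection defined as any new HSV, syphilis, chlamydia or gonorrhea infections during follow-up". Section 9.2.6, under Other Objective 2.4.2, first takes both cohorts as the analysis sample. It then states that Cox regression will compare STI incidence antepartum, postpartum and over the whole study "among women with no STIs at enrollment in Cohort 1 and Cohort 2, adjusting for baseline confounders".

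Section 6.2.1.1 schedules syphilis and HSV2 blood tests and chlamydia and gonorrhea tests at enrollment. Sections 6.2.1.7 and 6.4.2.1 and Appendices IIA and IIB repeat all four at Week 26 postpartum or early discontinuation, in both cohorts. The eligibility criteria (Sections 4.1.2 and 4.2.1) do not exclude women with any of these four infections. Section 3.3 adds: "Participants with a laboratory diagnosis consistent with an STI will be referred for or provided with treatment as indicated".

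The Primary SAP does not cover this objective. Its Section 1.1 says: "A separate SAP will provide outlines of analyses for other objectives and outcome measures not included in the Primary SAP". That later SAP is not among the documents.

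**The concern.** The endpoint is a composite of four infections, but the risk set uses one all-or-nothing condition. Being positive for one agent at entry is treated as not being at risk for the other three. A woman with HSV-2 only can still acquire syphilis, chlamydia or gonorrhea. A woman with chlamydia only can still acquire the other three. Their exit tests are scheduled and paid for, yet this comparison does not use the results.

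STI incidence is the laboratory counterpart to self-reported condomless sex within Objective 2.4.2. The discussion of behavioral disinhibition in Section 1.2 reads STI rates on PrEP against diagnoses at baseline. Removing every woman with a baseline diagnosis takes out a group that matters for that question. It also makes the estimate apply to a narrower population than the objective states, and it lowers the number at risk in a study with only 100 evaluable women planned in Cohort 2.

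**Working it through.** **1. The rule traced through.**

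| Status at entry | Agents she is negative for | In the STI risk set as written? |
|---|---|---|
| Negative for all four | 4 | Yes, for all four |
| HSV-2 only | 3 (syphilis, chlamydia, gonorrhea) | No, for any |
| Chlamydia only | 3 (HSV-2, syphilis, gonorrhea) | No, for any |

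No text in the protocol or Primary SAP makes the condition agent-specific. That HSV-2 persists is general knowledge rather than something the documents state, and the point does not need it.

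**2. Size of the risk set.** Section 9.2.4 assumes 300 evaluable women (200 and 100). It gives no event rate or power for STIs, so there is no planned figure to reproduce. Entry prevalence is not given either. Let *p* be the share with any of the four at entry, assumed equal in both cohorts. Then the risk set is 300 × (1 − *p*). This form needs no assumption about how the infections overlap.

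**3. What that does to power, for illustration only.** The nearest yardstick is Table 10 (safety outcomes): 10% in Cohort 2 against 23% in Cohort 1, 80% power, alpha 0.05, taken as two-sided. The normal approximation is

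power = Φ[(d − 1.96 × SE0) / SE1].

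With d = 0.13 and pooled proportion (10 + 46)/300 = 0.187:
- SE0 = √[0.187 × 0.813 × (1/100 + 1/200)] = 0.0477
- SE1 = √[0.09/100 + 0.1771/200] = 0.0423
- power = Φ(0.863) = 0.806, which agrees with the stated 80%.

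The same formula on the reduced numbers gives:

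| Assumed any-STI prevalence at entry | Cohort 1 / Cohort 2 | Total | Power, 10% vs 23% | Cohort 1 rate detectable at 80% power |
|---|---|---|---|---|
| 0% | 200 / 100 | 300 | 0.806 | 22.9% |
| 10% | 180 / 90 | 270 | 0.760 | 23.8% |
| 20% | 160 / 80 | 240 | 0.705 | 24.8% |
| 30% | 140 / 70 | 210 | 0.641 | 26.0% |
| 40% | 120 / 60 | 180 | 0.567 | 27.5% |
| 50% | 100 / 50 | 150 | 0.485 | 29.6% |
| 60% | 80 / 40 | 120 | 0.394 | 32.4% |

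The planned analysis is a Cox model, and the 10% and 23% are not STI rates. The table shows only how fast precision erodes.

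**4. What agent-specific risk sets would recover.** Take one assumed mix, with independent infections: HSV-2 20%, syphilis 2%, chlamydia 10%, gonorrhea 3%.
- As written: 300 × 0.80 × 0.98 × 0.90 × 0.97 = 205 women, for every agent.
- Excluded for HSV-2 alone: 300 × 0.20 × 0.98 × 0.90 × 0.97 = 51 women, all still at risk for the other three.
- Agent-specific: HSV-2 240, syphilis 294, chlamydia 270, gonorrhea 291.
- Composite: only women positive for all four would drop out, 300 × 0.20 × 0.02 × 0.10 × 0.03 = 0.004, in effect none.

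**The case against.** **Follow-up is untouched.** A reader might infer that these women stop being followed. They do not. Appendices IIA and IIB schedule the exit tests for them, and the restriction is not applied to the condomless-sex or HIV incidence analyses. Only the STI incidence model is affected. This stands.

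**Restriction controls confounding.** A reader might infer that the rule biases the cohort comparison, particularly if women choosing PrEP have more STIs at entry. The documents do not support that. They give no entry prevalence by cohort, and restricting both cohorts to one level of a baseline risk factor is a recognised way to make them more alike. Unequal exclusion does not by itself create bias. What is lost is precision and generalizability. This stands too.

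**The text is an outline.** Section 9.2.6 refers to an SAP for detail, the objective is not primary, and its wording speaks of incidence rates in the plural, so agent-specific rates in agent-negative women are a possible reading. But the restriction is written once, without reference to agent. A later SAP that follows it would inherit the problem, and having two readings is itself a reason to settle the wording.

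**Treated infections are hard to classify.** Routine laboratory STI tests fall only at entry and exit, treatment may be by referral, and no test of cure or syphilis titre is scheduled. A same-agent positive at exit could be persistence or reinfection. This rules out counting such positives as new in the main analysis. It is no reason to exclude the woman from the agents she was negative for.

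**Conclusion.** The mismatch between a four-infection endpoint and an all-STI-free risk set is real in the protocol as written, and it holds at any non-zero entry prevalence. The consequence is fewer women at risk and an estimate for a subset of those named in Objective 2.4.2. It is not a demonstrated bias, and it is not a loss of follow-up.

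The size is conditional. With any-STI prevalence at entry assumed at 10% to 60% and equal across cohorts, the risk set is 270 to 120 instead of 300. No single percentage should be carried forward as an estimate. Figures built from separate HSV-2 and curable-STI prevalences also depend on overlap: at 30% and 20%, independence excludes 1 − 0.70 × 0.80 = 44%, while complete overlap excludes 30%.

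This is an inexpensive improvement to a non-primary objective. The later SAP, which was not available, may already address it.

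**What to change.** In Section 9.2.6 and in the SAP for the other objectives, replace the restriction to STI-free women with these rules:

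- Analyse each infection among women who tested negative for that infection at entry.
- Define the composite as a new infection with any agent for which the woman was negative at entry.
- Include entry STI status as a covariate instead of using it as an exclusion.
- Report same-agent positives after a treated entry infection only as a sensitivity analysis.
- Tabulate entry STI prevalence by cohort, so that the reader can see how many women each definition removes.

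The cost is wording and programming; no visit, specimen or test is added. The drawback is that the composite covers different agents for different women. Agent-specific results should therefore be shown beside it, and the analysis limited to women with no STI at entry should be kept as a second sensitivity analysis. That also preserves the comparison now planned.

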#### **Other Objective 2.4.3:**

Among women and infants who acquire HIV infection, the proportion with antiretroviral drug resistance to FTC/TDF-at the time of HIV diagnosis will be calculated. In addition, testing of entry specimens will be performed to see if resistance was transmitted or selected by the study drugs.

#### **Other Objective 2.4.4:**

Student t tests will be used to compare the mean maternal bone mineral density of the lumbar spine and of the hip for Cohort 1 and Cohort 2 at delivery and week 26 post-delivery.

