#### *Bone demineralization*

Consistent with data on reduced bone mineral density (BMD) among HIV-infected adults on ARVs, PrEP use has been associated with an approximate 1% reduction in BMD among trial participants (11, 74). The effect on BMD was shown to be reversible in young African women adherent to PrEP in the VOICE trial with a follow-up dual-energy x-ray absorptiometry (DXA) scan 48 weeks after stopping study drug (75). Of special note is that the women studied in these trials were not lactating. There are no data at this time to evaluate the additive effect of lactation on bone loss due to PrEP. The bone mineral resorption required for breastmilk production results in a 3-5% reduction in BMD over six months of lactation that is generally restored within six months of cessation of breastfeeding. Preliminary data from IMPAACT P1084s – a sub study of PROMISE conducted at eight African sites – revealed a decline in BMD at 74 weeks postpartum in HIV-infected women receiving TDF-based cART who breastfed for a mean of 61 weeks when compared to women not receiving cART (76). The mean difference at the lumbar spine was -3.16% (95% CI -4.44, -1.87) and -2.33% (-3.23, -1.42) at the hip (both p-values<0.001). The IMPAACT 2009 study provides an important opportunity to study the effect of PrEP use and lactation on bone mass in young women who are yet to achieve peak bone mass.

For U.S. infant populations, Siberry and colleagues reported reduced bone mineral content of uncertain clinical significance among newborns who had been exposed *in utero* to TDF taken by their HIV-infected mothers (77). However, more recent work from Cape Town, South Africa found that fetal exposure to TDF did not appear to alter fetal long bone growth (78). IMPAACT P1084s found that *in utero* exposure to TDF-containing cART was not associated with lower bone mineral content among HIV-exposed newborns, when compared to other cART regimens. However, the data suggested a substantial and significant bone mineral content reduction in newborns exposed to maternal triple cART when compared to maternal zidovudine monotherapy (79). The effect of exposure to *in utero* and postnatal ARVs on long term infant bone health, growth and development remains so far still uncertain. Six-month longitudinal outcomes are currently being analyzed for P1084s.

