### **1.5 Hypotheses for the PrEP Comparison Component**

- At least 75% of women who opt to initiate PrEP will achieve a high level of adherence throughout pregnancy, as measured by adequate TFV-DP concentrations in DBS specimens.
- The rate of maternal and infant adverse events (including adverse pregnancy outcomes) will be higher among mother-infant pairs in which the mother initiates PrEP during pregnancy than in pairs in which the mother declines PrEP.
- The mean bone mineral density for the lumbar spine and hip at baseline and at Week 26 postpartum will be lower among women who initiated PrEP during pregnancy than among women who decline PrEP.

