## 6.10 Maternal DXA Scans

Maternal participants in the PrEP Comparison Component will undergo DXA scans of the hip and lumbar spine at their Labor & Delivery Visit and Week 26 postpartum as well as early discontinuation visits, if applicable. Scans will be performed according to standardized procedures described in the study-specific MOP. Scan images will be transferred electronically for centralized reading and results will be transmitted electronically from the central readers to the Data Management Center (DMC); however, if a maternal participant experiences a bone fracture subsequent to her scan, the result of her scan will be provided to the site as soon as available.

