10.0%	(6.2, 15.0)	(4.9, 17.6)
15.0%	(10.4, 20.7)	(8.6, 23.5)
20.0%	(14.7, 26.2)	(12.7, 29.2)
30.0%	(23.7, 36.9)	(21.2, 40.0)

The study allows adequate power to detect moderate cohort differences from 8.5% to 16%, depending on the true background rate of the event, as summarized below in **Table 10**. The table shows minimum detectable differences in safety outcomes between Cohort 1 and Cohort 2 which could be achieved with 80% power and alpha=0.05. For example, based on a sample size of 200 in Cohort 1, and assuming a 2:1 enrollment among women agreeing to and declining PrEP, differences of at least 13% will be detectable between the two cohorts in the proportion of maternal adverse events for events with a 10% background rate (10% in Cohort 2, 23% in Cohort 1).

**Table 10: Minimum detectable differences in safety outcomes based on evaluable sample size of 300 for Cohort 1(n=200) and Cohort 2 (n=100), 80% power, alpha=0.05**

% with event in Cohort 2 (N=100)	% with event in Cohort 1 (N=200)	Odds Ratio
2%	10.5%	5.8
5%	15.6%	3.5
10%	23%	2.67
15%	29%	2.36
20%	35%	2.19
25%	41%	2.10

To address primary objective 2.3.2, the mean bone mineral content of infants at birth and at age 26 weeks will be estimated and differences in mean bone mineral content between infants in Cohort 1 and Cohort 2 will be evaluated using two sample t tests. **Table 11** shows the statistical

power the study would have to detect a range of estimated differences in means. For example, with a sample size of 200 in Cohort 1 and 100 in Cohort 2 this study will be able to detect differences in mean bone mineral content of at least 0.35 SD with 80% power. Based on the SMARTT study in the U.S., assuming a standard deviation of 16.6 (77) this would be equivalent to a difference in means of 5.81g. Assuming a standard deviation of 14.9 found in the P1084s study (79) this would be equivalent to a difference in means of 5.22 g.

**Table 11: Estimated Power to Detect the Mean Differences in Infant Growth Outcomes Infant DXA, Whole Body Bone Mineral Content (BMC) (g) at Birth (Mean=63.8, SD=16.6)\*\***

Difference to be Detected	Effect Size (SD)	Power (based on sample sizes*)		
		N1=200 N2=100	N1=180 N2=90	N1=160 N2=80
4% (of 63.8)	2.55 (16.6)	24%	22%	20%
5%	3.19	35%	32%	29%
6%	3.83	47%	43%	39%
7%	4.47	59%	55%	50%
8%	5.10	71%	66%	61%
9%	5.74	80%	76%	71%
10%	6.38	88%	84%	80%
0.25*SD	4.15	53%	49%	44%
0.30*SD	4.98	68%	64%	59%
0.35*SD	5.81	81%	77%	72%
0.40*SD	6.64	90%	87%	83%
0.45*SD	7.47	96%	94%	91%

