0.50*SD	8.30	98%	97%	95%
0.75*SD	12.45	> 99%	> 99%	> 99%

\*Sample Sizes: N1 -- Cohort 1 (PrEP), N2 – Cohort 2 (no PrEP)

\*\*Data were from PHACS SMARTT Study (Siberry, 2015)

To address other objective 2.4.4, the mean bone mineral density of the lumbar spine and of the hip of women at delivery and at 26 weeks post-delivery will be estimated and differences in mean bone mineral density between women in Cohort 1 and Cohort 2 will be evaluated using two sample t tests. Table 12 shows estimated statistical power to detect a range in differences in mean maternal bone mineral density that the study could detect given different sample sizes. For example, with a sample size of 300 (200 PrEP and 100 no PrEP) the study would have at least 80% power to detect a minimum 4% difference in mean BMD and .35 SD difference in means between groups at delivery and 26 weeks postpartum.

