**Table 12: Estimated Power to Detect the Mean Differences in Maternal Growth Outcomes**  
**Maternal DXA, Whole Body Bone Mineral Content (BMC) (g)**  
**(Mean=0.979, SD=0.111)\*\***

BMD	Difference to be Detected	Effect Size (SD*)	Power (based on sample sizes**)		
			N1=200 N2=100	N1=180 N2=90	N1=160 N2=80
Lumbar Spine	1% (of 0.979*)	0.0098 (0.111*)	11%	10%	10%
	2%	0.0196	30%	28%	25%
	3%	0.0294	58%	53%	49%
	4%	0.0392	82%	78%	73%
	5%	0.0490	95%	93%	89%
	6%	0.0587	99%	98%	97%
	0.10*SD	0.0111	13%	12%	11%
	0.15*SD	0.0167	23%	21%	19%
	0.20*SD	0.0222	37%	34%	31%
	0.25*SD	0.0278	53%	49%	44%
	0.30*SD	0.0333	69%	64%	59%
	0.35*SD	0.0389	81%	77%	72%
	0.40*SD	0.0444	90%	87%	83%
Total Hip	1% (of 0.968*)	0.0097 (0.119*)	10%	10%	9%
	2%	0.0194	26%	24%	22%
	3%	0.0290	51%	47%	43%
	4%	0.0387	75%	71%	66%
	5%	0.0484	91%	88%	84%
	6%	0.0581	98%	97%	94%
	0.10*SD	0.0119	13%	12%	11%
	0.15*SD	0.0179	23%	21%	19%
	0.20*SD	0.0238	37%	34%	31%
	0.25*SD	0.0298	53%	49%	44%
	0.30*SD	0.0357	68%	64%	59%
	0.35*SD	0.0417	81%	77%	72%
	0.40*SD	0.0476	90%	87%	83%

\*Data were from JAIDS (Mirembe, 2015): mean (SD) = 0.979 (0.111) for lumbar spine; mean (SD) = 0.968 (0.119) for total hip.

\*\*Sample Sizes: N1 -- PrEP Arm, N2 -- non-PrEP Arm

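### Maternal BMD (objective 2.4.4) is compared only as unadjusted levels at delivery and at Week 26; the protocol and Primary SAP plan no analysis of within-woman change, though both scans are scheduled for every woman

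*Protocol*

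**What the plan says.** - **Analysis.** Protocol section 9.2.6, under Other Objective 2.4.4, consists of one sentence: "Student t tests will be used to compare the mean maternal bone mineral density of the lumbar spine and of the hip" for the two cohorts at the two times. Section 9.2.4 agrees: "differences in mean bone mineral density between women in Cohort 1 and Cohort 2 will be evaluated using two sample t tests". Table 6 lists mean BMD at each time as the outcome. No covariates are named.
- **Scans.** Under section 6.10, women "will undergo DXA scans of the hip and lumbar spine at their Labor & Delivery Visit and Week 26 postpartum". No DXA is scheduled at entry. Section 5.1.2.2 starts PrEP in Cohort 1 on the day of enrollment, so the first scan follows antenatal exposure.
- **Hypothesis.** Section 1.5 reads: "The mean bone mineral density for the lumbar spine and hip at baseline and at Week 26 postpartum will be lower" in women who started PrEP. It gives no effect size.
- **Background.** Section 1.2 reports that "PrEP use has been associated with an approximate 1% reduction in BMD among trial participants", and notes that those women were not lactating. It also cites differences of -3.16% (spine) and -2.33% (hip) at 74 weeks postpartum in breastfeeding women with HIV on TDF-based cART. It says that no data exist on how lactation adds to PrEP-related bone loss, and it presents this study as a chance to learn about PrEP, lactation and bone mass.
- **Power.** Table 12 is titled "Estimated Power to Detect the Mean Differences in Maternal Growth Outcomes". Its subtitle refers to whole-body bone mineral content, but its rows are spine and hip BMD.
- **SAP.** The Primary SAP omits objective 2.4.4. Its section 1.1 assigns other objectives to a separate SAP.

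**The concern.** The gap named in the background is bone loss during lactation on PrEP. In this design that is a change between the delivery scan and the Week 26 scan, and two separate level comparisons do not estimate it.

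Level comparisons have two further weaknesses here. First, the spread of BMD between women is large beside any plausible effect: the SD is 0.111/0.979 = 11.3% of the mean at the spine and 0.119/0.968 = 12.3% at the hip. Second, women chose their cohort, so stable differences in bone mass between the cohorts go straight into the contrast. Section 9.2.1 recognises confounding in general, and the analyses of pregnancy outcomes, adverse events and sexual behavior adjust for it; the BMD analysis does not.

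A null result would therefore say little about postpartum bone loss on PrEP, and a positive one could reflect who chose PrEP.

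**Working it through.** **Inputs from the documents.** Spine mean (SD) 0.979 (0.111) and hip 0.968 (0.119), from the Table 12 footnote. Sample size: "with a sample size of 300 (200 PrEP and 100 no PrEP"). Alpha is 0.05, from the text on Table 10 ("which could be achieved with 80% power and alpha=0.05"), because Table 12 states none. A two-sided test is assumed.

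**Input not in the documents.** The correlation r between a woman's delivery and Week 26 BMD. I assume 0.8, 0.9 and 0.95, and show 0.5 as a low case.

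**Step 1: reproduce Table 12.** Power comes from the noncentral t distribution with 298 df and noncentrality Δ / (SD × √(1/200 + 1/100)), where the root is 0.1225. For a 1% spine difference: 0.00979 / (0.111 × 0.1225) = 0.72, so power is 11.1%.

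| Difference | Spine, Table 12 | Spine, recomputed | Hip, Table 12 | Hip, recomputed |
|---|---|---|---|---|
| 1% | 11% | 11.1% | 10% | 10.2% |
| 2% | 30% | 30.0% | 26% | 26.3% |
| 3% | 58% | 57.7% | 51% | 51.0% |
| 4% | 82% | 81.9% | 75% | 75.4% |

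The table reproduces. A one-sided test does not fit (17.8% and 16.3% at 1%). Section 9.2.4 claims at least 80% power for a 4% difference without naming a site; by Table 12 that is true of the spine only.

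**Step 2: level comparison at the cited effects.** The smallest difference with 80% power is 0.343 SD: 0.343 × 0.111/0.979 = 3.9% at the spine and 0.343 × 0.119/0.968 = 4.2% at the hip. Both exceed every between-group effect cited in section 1.2. At the cited cART effects, power is 62% (spine, 3.16%) and 34% (hip, 2.33%).

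**Step 3: within-woman change.** With equal SDs at the two times, SD of change = SD × √(2(1 − r)). At r = 0.8, 0.9 and 0.95 this gives 0.0702, 0.0496 and 0.0351 (spine) and 0.0753, 0.0532 and 0.0376 (hip). Percent change is approximated by change divided by the mean. The test and the numbers (200 and 100) are as in step 1.

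| Postpartum difference | Level | r = 0.8 | r = 0.9 | r = 0.95 |
|---|---|---|---|---|
| Spine 1% | 11% | 21% | 36% | 62% |
| Hip 1% | 10% | 18% | 32% | 55% |
| Spine 2% | 30% | 62% | 89% | >99% |
| Hip 2% | 26% | 55% | 84% | 99% |

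At r = 0.5 the SD of change equals the level SD, so nothing is gained. For a 1% difference, 80% power needs r of about 0.97.

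**Step 4: part of the effect before delivery.** If only half of a 1% effect falls after delivery, change-score power is 8.8%, 12.6% and 20.6% (spine) and 8.2%, 11.5% and 18.2% (hip) at r = 0.8, 0.9 and 0.95.

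**The case against.** Several objections have force.

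- **The planned tests match the stated objective.** Objective 2.4.4 and the section 1.5 hypothesis concern density, not loss. This stands: the tests do not mis-measure the objective as written. What they miss is the postpartum loss that the background raises.
- **A reader might infer that the protocol expects a 1% effect and so planned for 11% power.** It does not say so. The 1% is a cited finding in non-lactating women, the larger cART effects are cited beside it, and the power text targets 4% or 0.35 SD.
- **A reader might infer that change will never be analysed.** That cannot be said. Section 9.2.6 is an outline, this is an Other objective meant for later publications, and its SAP was not available.
- **A reader might want change, or Week 26 BMD adjusted for delivery BMD, as the main measure.** The design argues against it. There is no pre-PrEP scan, so the delivery value already carries any antenatal effect, and conditioning on it or subtracting it removes that part. For early enrollees antenatal exposure can be long: section 6.2.1.3 allows antepartum visits out to study Week 36.
- **The power gain is not like for like.** This also stands. Step 3 places the whole difference after delivery; step 4 shows how quickly power falls otherwise.
- **Scheduled scans are not completed scans.** The SAP defines evaluable as completing Week 26, not as having both scans, and Appendix X foresees DXA scheduling problems. Using 200 and 100 for the paired analysis is optimistic.
- **Limited power is disclosed.** Section 9.2.1 says so for safety outcomes, and Table 12 prints the low values. Disclosure does not explain why the paired data go unused.

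**Conclusion.** The point holds as an omission. The protocol and the Primary SAP plan only unadjusted level comparisons for maternal BMD and make no use of the paired scans. With 200 and 100 women, the level comparison has 10-11% power at the cited 1% and about 62% (spine) and 34% (hip) at the cited cART effects.

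A change analysis removes stable differences between women and can raise power substantially for a postpartum difference of about 2%, provided r is 0.8 or more. It does not rescue a 1% effect unless r is about 0.97, and it covers only loss after delivery. It belongs beside the level comparisons, not in their place. The results assume a two-sided 0.05 test, equal SDs at both times and complete pairs; r is an assumption throughout.

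Separately, *baseline* in section 1.5 has no pre-exposure scan behind it. This is not a primary objective, so the consequence is limited to what the study can say about maternal bone.

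**What to change.** 1. In section 9.2.6 and in the separate SAP for other objectives, add the between-cohort difference in percent change in BMD from delivery to Week 26, at spine and hip, adjusted for measured confounders. Label it as an additional analysis of postpartum bone loss.
2. Keep the Week 26 level comparison, because it alone includes both antenatal and postpartum effects. The delivery comparison can stay as planned.
3. In section 1.5, replace *baseline* with *delivery*.
4. State the assumed correlation, or the SD of change, with any power figure given for the new analysis.

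The cost is wording and analysis time; no scan or visit is added. Women with only one scan drop out of the change analysis, so report how many do in each cohort. The result must be described as postpartum loss only.
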